7.2.1. Electronic Diary

Patients will be issued an eDiary to record all bleeding events and all doses of factor concentrates administered during the conduct of the study. Entries are to be made in a timely manner, and it is preferred that doses are entered immediately upon administration or within 24 hours. Patients will be prompted to enter bleeding location, severity, causality (spontaneous or traumatic), doses of factor concentrates, and reasons for dosing (prophylaxis, treatment of a bleed, and preventive dose for anticipated activity). Training of patients should be documented in the appropriate source record.

The Sponsor or an independent delegate will review diary entries for data quality to identify issues such as subjects who may need retraining on diary use and timely entry of bleeding episode information.

Bleeding episodes will be recorded by the patient in the eDiary, and reviewed by the Investigator (and Sponsor or independent delegate) continuously for the study duration. The site will contact the patient at a minimum interval of every 2 weeks per schedule of assessments to review diary records and ensure that the patient is utilizing the device appropriately.

Sites will be notified when patients enter initial treatments for bleeding events into their eDiaries. If the dose amount exceeds the recommended dose according to the bleeding management plan, the patient must be contacted as soon as possible, preferably within 24-48 hours of receiving the alert. At the time of contact the patient's clinical condition will be reviewed along with the dose and efficacy of the treatment given, and the Investigator will provide appropriate guidance regarding further management of the bleeding episode. The site will also receive an alert, and must make contact with the patient as soon as possible if a third dose of product is administered for a single bleed, to review clinical condition, the need for further therapy, and appropriate ongoing management of the bleeding episode required to achieve hemostasis.

In addition, patients will be instructed to contact the site if they feel they need to administer factor concentrates at a higher dose level or higher frequency than their bleeding management plan recommends, or if more than two doses are required to achieve hemostasis.

Complete instructions will be provided in the Study Manual.

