1.5. Benefit-Risk Assessment

Based on the available clinical data (see Section 1.2.2), fitusiran administered subcutaneously as a once-monthly fixed-dose regimen, may be able to offer potentially reduced bleeding rates for patients receiving factor concentrate or BPA treatment prophylactically or on-demand. Further, the pharmacodynamic profile of fitusiran results in consistent reduction of AT and therefore may provide more consistent increase in thrombin generation and hemostatic protection throughout the dosing interval. The clinical experience to date suggests that in hemophilia A or B patients, with or without inhibitors, fitusiran treatment is associated with reductions in AT, increases in thrombin generation, and reduction of the number of bleeding episodes.

Given the mechanism of action of fitusiran, mode of administration, and available safety data, the possible risks associated with the use of fitusiran include thrombosis, liver transaminase abnormalities, and injection site reactions (ISRs). Due to the underlying pro-hemostatic effect of fitusiran, the concomitant treatment of breakthrough bleeding episodes with factor or BPA particularly at doses higher than recommended in the protocol may confer an increased risk of thrombosis. For summary of the completed Phase 1 study, and preliminary interim results from the Phase 1/2 extension study, see Section 1.2.2; further details of fitusiran studies are presented in the Investigator's Brochure.

This clinical protocol has exclusion criteria intended to minimize the risk of thrombosis, liver transaminase abnormalities, and serious ISRs. With respect to the risk of thrombosis, the protocol includes detailed guidance and oversight on treatment of breakthrough bleeding episodes with reduced factor/BPA dosing (Section 6.3.1), and management of operative procedures that occur while patients are on fitusiran (Section 6.6). The protocol also excludes patients with evidence of liver disease (including active viral hepatitis) and stipulates ongoing monitoring for elevated transaminases (Section 6.2.3.1). The safety of trial patients will be overseen by an independent DMC (Section 4.7).

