6.3.1. Management of Bleeding Episodes

The occurrence of bleeding episodes is a typical characteristic of hemophilia; [2, 5, 6] bleeding episodes will be recorded as an efficacy assessment of fitusiran and will not be considered as AEs unless the criteria for SAEs are met (see AEs definitions in Section 7.5.6.1). Bleeding episodes will be recorded in the eDiary. For bleeding episodes in which there was no factor concentrate infusion or other type of intervention employed, the reason the bleeding episodes were untreated will be recorded in the eDiary (see Section 7.2.1).

Investigators will establish and provide instructions for an individualized bleed management plan based on the guidelines in Table 4 for each patient.

The bleed management plan should be reviewed by the Investigator or designee with the patient at each clinic visit (and via telephone contact every 2 weeks between clinic visits) and updated as necessary.

Doses of rFVIIa and aPCC are included for completeness. It is expected that these non-inhibitor patients will be routinely managed with FVIII and FIX.

6.3.1.1. Bleeding Episode Management Recommendations for Patients in the On-Demand Treatment Arm (Patients Not Receiving Fitusiran)

For patients not receiving fitusiran (on-demand arm), bleeding management therapy with factor concentrate will be managed based on the local standard practice for treating hemophilia patients without inhibitors, as routinely administered by the physician. Where clinical circumstances allow, it is recommended that the patient contact the Investigator for all events that may be suspected to be or characteristic of a bleeding episode. If adequate hemostasis does not occur after two doses of factor concentrate, the patient should contact the site for further instruction. If the patient feels the need to administer doses higher than the patient's bleeding episode management plan recommends, or at a higher frequency, it is recommended that the patient contact the site. See Section 7.2.1 regarding patient use of the eDiary and site alerts that will assist in this process.

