| Repeat dose instructions | Mandatory to call the clinical study center prior to second dose Consider evaluation and treatment at the clinical study center (see Section 6.4) | | | | Mandatory to call site prior to third dose |
| | Should not repeat in less than 24 hours | Should not repeat in less than 24 hours | Should not repeat in less than 5-7 days | Should not repeat in less than 24 hours | Should not repeat in less than 2 hours |
| | Should be seen at site within 48-72 hours if more than 2 doses are required (see Schedule of Assessments for assessments) | | | | Should be seen at site within 48-72 hours if more than 3 doses are required |
| For situations requiring higher doses, more frequent administration, multiple repeated doses, discussion with study Medical Monitor and Clinical Advisor is recommended, and AT replacement should be considered. | | | | | |
| Do not use antifibrinolytics in combination with factor or BPA. | | | | | |

Note: Doses of rFVIIa and aPCC are included for completeness. Adjunctive management of bleeding episodes should be carried out per standard of care. It is expected that these non-inhibitor patients will be routinely managed with FVIII and FIX.

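### Section 7.2.1 tells all patients to contact the site once more than two doses are needed, one dose later than the call Table 4 makes mandatory for fitusiran patients using FVIII, FIX or aPCC

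*Protocol*

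**What the plan says.** Protocol Section 7.2.1 describes three eDiary-driven contacts from the site side. First, "Sites will be notified when patients enter initial treatments for bleeding events into their eDiaries". Second, the site must contact the patient when a dose exceeds what the bleed management plan recommends. Third, the site is alerted and must make contact "if a third dose of product is administered for a single bleed".

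The same section tells patients to contact the site if they feel they need a dose level above the plan, or a "higher frequency than their bleeding management plan recommends", "or if more than two doses are required to achieve hemostasis". None of this is separated by arm or product.

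Section 6.3.1.1, for the on-demand arm, has the same threshold: "If adequate hemostasis does not occur after two doses of factor concentrate, the patient should contact the site for further instruction".

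For the fitusiran arm from Day 8, Section 6.3.1.2 says the patient must call before a second dose of FVIII, FIX or aPCC, or before a third dose of rFVIIa. Table 4 repeats this: "Mandatory to call the clinical study center prior to second dose" for the first group of products and "Mandatory to call site prior to third dose" for rFVIIa.

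**The concern.** The same fitusiran patient meets two contact thresholds in one protocol. Section 7.2.1 asks for contact when a third dose is needed. Section 6.3.1.2 and Table 4 require it before the second, for FVIII and FIX, which the protocol expects these patients to use routinely. Section 6.3.1.1 refers the reader to 7.2.1 for the diary and site alerts; Section 6.3.1.2 has no such reference. The eDiary section therefore reads as if written around the on-demand rule.

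At stake is a safety control. Section 6.5 says thrombotic risk on fitusiran may rise with concurrent factor or BPA. Section 6.3.1.2 lists repeated doses among the circumstances in which to consider consulting the Medical Monitor and Clinical Advisor about AT replacement. Section 1.5 relies on guidance and oversight of bleed treatment to limit that risk. Because factor can be given at home, the patient's instruction and the eDiary alert are the controls nearest in time to the repeat dose.

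**Working it through.** The plan gives no figure to reproduce. The check sets the contact rules side by side.

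| Place in protocol | Arm and period | Product | Point at which contact applies |
|---|---|---|---|
| 7.2.1, patient instruction | Not separated | Factor concentrates | More than two doses needed, so at dose 3 |
| 7.2.1, site alert | Not separated | Any product | After dose 3 has been given |
| 6.3.1.1 | On-demand | Factor concentrate | After two doses without adequate hemostasis |
| 6.3.1.2 | Fitusiran, Days 1 to 7 | Factor or BPA | Before administering |
| 6.3.1.2 and Table 4 | Fitusiran, Day 8 on | FVIII, FIX, aPCC | Before dose 2 (mandatory) |
| 6.3.1.2 and Table 4 | Fitusiran, Day 8 on | rFVIIa | Before dose 3 (mandatory) |
| 6.3.1.2 and Table 4 | Fitusiran, Day 8 on | FVIII, FIX, aPCC | More than two doses: site visit in 48 to 72 hours |

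1. **Patient instruction, FVIII and FIX.** Dose 3 in 7.2.1 against dose 2 in Table 4: 3 − 2 = 1 dose later. The same holds for aPCC if the 7.2.1 sentence, which speaks of factor concentrates, is taken to cover it.
2. **Patient instruction, rFVIIa.** Dose 3 in both places, so no difference in dose number: 3 − 3 = 0.
3. **Site alert.** It fires on a dose already given, whereas Table 4's call is a duty before dosing. For FVIII, FIX and aPCC the alert coincides with Table 4's separate site-visit step for more than two doses. For rFVIIa it follows the dose that needed the prior call.
4. **Second dose.** Of the three site-side contacts in 7.2.1, one is tied to the initial treatment, one to dose amount and one to the third dose. None is tied to a second dose as such.
5. **Who and how long.** Section 1.3 plans 80 patients in the fitusiran arm. Day 8 to Day 246, the end of the analysed treatment period, is 246 − 8 + 1 = 239 of 246 days.

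**The case against.** The strongest reply is that the rules are compatible. A fitusiran patient who calls before dose 2 also satisfies 7.2.1. Section 7.2 closes by assigning bleed management to Section 6.3.1, and the 7.2.1 contact sentence is worded as an addition. Each patient has an individual plan based on Table 4, reviewed at visits and by telephone every two weeks, and fitusiran patients get a separate plan for Day 8 onward. Section 6.3.1.2 also recommends contact before every dose. All of this stands: the two passages do not make compliance impossible. It does not remove the mismatch, because the 7.2.1 sentence taken alone leaves out a call that the protocol words as mandatory.

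Three stronger readings are tempting, and the documents do not support them.

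- *The third-dose alert is set wrongly for the fitusiran arm.* It fits that arm's own step for more than two doses. As a check on recorded doses, with entry preferred immediately or within 24 hours, it could not enforce a call before dosing in any case.
- *Missed calls would pass unnoticed.* The site learns of the initial treatment, and diary entries are reviewed continuously. The bleed management review in Table 1 (footnote t), at each visit and every two weeks between visits, asks whether appropriate site contact took place. What remains is that these checks find a missed call afterwards; none is described as prompting it.
- *The gap can be sized as excess factor dose.* That needs an assumption about what the individual plan allows, and the same two doses could follow a compliant call. Section 1.5's warning is also mainly about dose size ("particularly at doses higher than recommended in the protocol may confer an increased risk of thrombosis") rather than a second dose within range.

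The higher-frequency trigger in 7.2.1 might catch a second dose if the individual plan is written that way. The Study Manual, which is to hold the complete eDiary instructions, might contain an arm-specific prompt. Neither document is available to check.

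**Conclusion.** The inconsistency is real and limited. The patient-contact threshold in 7.2.1 is not specific to arm or product. For fitusiran patients from Day 8 it comes one dose later than the mandatory call for FVIII and FIX. No described eDiary alert is tied to the second dose, so a missed call would come to light only through diary review or the visit and two-weekly bleed management review.

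This rests on the protocol text alone and assumes that neither the individual plan nor the Study Manual already supplies the missing prompt. How often a second dose would be taken without a call cannot be estimated from the documents. The point does not touch sample size, power or multiplicity. It is worth correcting because it concerns oversight of a risk the protocol itself names. The documents give no basis here for calling either threshold the wrong one, and none is offered.

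**What to change.** Reconcile the contact instruction in Section 7.2.1 with Sections 6.3.1.1 and 6.3.1.2 and Table 4, stating it by arm and by product, or replace it with a cross-reference to those sections. Align the eDiary repeat-dose alert or prompt with whichever thresholds the sponsor confirms, and carry the same wording into the Study Manual and the individual bleed management plans. The choice of threshold is the sponsor's; what matters is that every place gives the same patient the same instruction.

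The cost is a wording change, an arm-specific alert setting in the eDiary, and a few more alerts for sites to handle.

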7.3. Pharmacodynamic Assessments

In this study AT activity level and thrombin generation will be collected as measurements of PD effect. These measurements will be collected and analyzed centrally for research purposes. As interpretation is uncertain, TG thrombin generation results will not be used to adjust dosing of fitusiran or guide other elements of study conduct or clinical management and will not be shared with sites until after study completion. If clinical circumstances arise for which AT activity levels are required to guide patient care, local laboratory assessments may be drawn.

7.3.1. Antithrombin Activity

AT activity level will be assessed according to the Schedule of Assessments (Table 1); samples will be collected within 4 hours prior to dosing. Antithrombin levels will be determined by validated assay. Antithrombin protein may be measured in a subset of plasma samples for correlation. Results will be collected and interpreted centrally.

In the fitusiran treatment arm patients who do not enroll in the extension study, following final fitusiran dose, AT activity level will be monitored at monthly intervals until returning to an activity level of approximately 60% (per the central laboratory) or per Investigator discretion in consultation with the study Medical Monitor.

7.3.2. Thrombin Generation

Thrombin generation will be assessed according to the Schedule of Assessments (Table 1) using a functional assay per the Laboratory Manual, and will be collected and interpreted centrally.

7.3.3. Exploratory Analyses

Except where prohibited by local or national regulations, in consented patients, plasma, serum, and urine samples may be archived and used for analyses of exploratory biomarkers related to the metabolic profiling or effects of fitusiran and for the development of modified thrombin generation assays, and may also be archived for use in other exploratory analyses related to hemophilia and its complications.

In addition, where permitted in consented patients, serum samples may be used for analysis of circulating RNA, including the assessment of cleaved AT RNA, and a sample of DNA may be obtained and archived to permit potential confirmation of hemophilia mutation or genotyping of hemophilia modifier genes or genes that may modify the effects of fitusiran.

7.4. Pharmacokinetic Assessments

Blood samples will be collected for assessment of PK including metabolites (as necessary) in all fitusiran arm patients according to the collection schedule presented in Table 7 on the days specified in the Schedule of Assessments (Table 1).

Blood must be aliquoted and processed as plasma for PK analysis. All plasma concentration data (Table 7 and Table 8) will be summarized and analyzed using a population PK approach.

In addition, plasma PK (Table 8, which includes those time points in Table 7) will be evaluated in East Asian patients in the fitusiran arm at East Asian sites (defined as patients from sites in China, Japan, South Korea, and Taiwan), and there will be pooled urine collection for urine PK analysis also in these patients (Table 9).

The concentration of fitusiran will be determined using a validated assay. Full details regarding the processing, shipping, and analysis of the samples will be provided in the Laboratory Manual.

7.5. Safety Assessments

The assessment of safety during the course of the study will consist of the surveillance and recording of AEs, including SAEs, recording of concomitant medication and measurements of vital signs, weight and height, physical examinations, ECG findings, and laboratory tests.

Safety data will be periodically reviewed over the course of the study by the DMC as described in Section 4.7.

7.5.1. Vital Signs

Vital signs will be measured as specified in the Schedule of Assessments (Table 1) and will include blood pressure, heart rate, body temperature, and respiratory rate. Vital signs will be measured predose in the seated or supine position, after the patient has rested comfortably for 10 minutes.

Body temperature in degrees Celsius will be obtained via oral, tympanic, or axillary methods. Heart rate will be counted for a full minute and recorded in beats per minute, and respiration rate will be counted for a full minute and recorded in breaths per minute.

For the safety of the patient, additional vital sign assessments may be added at the discretion of the Investigator.

Vital signs results will be recorded in the eCRF.

7.5.2. Weight and Height

Height will be measured in centimeters. Body weight will be measured in kilograms. Height and body weight measurements will be collected as specified in the Schedule of Assessments (Table 1) and will be recorded in the eCRF.

7.5.3. Physical Examination

Full and directed physical examinations will be conducted according to the Schedule of Assessments (Table 1); if a physical examination is scheduled for a dosing visit, it should be conducted prior to dosing.

Full physical examinations will include the examination of the following: general appearance; head, eyes, ears, nose, and throat; respiratory, cardiovascular, gastrointestinal, musculoskeletal, and dermatological systems; thyroid; lymph nodes; and neurological status.

Directed physical examinations will include examination of the following systems with attention to evaluation for signs and symptoms of thrombosis, bleeding, and arthropathy: neurologic, chest/respiratory, heart/cardiovascular, dermatological/skin, gastrointestinal/liver, and musculoskeletal/extremities. Other organ systems may be evaluated as indicated by patient

symptoms. In patients undergoing a surgical procedure, a directed physical examination will also be performed as specified in the Perioperative Schedule of Assessments (Table 10).

Physical examination notes regarding any observed abnormalities will be recorded on the eCRF.

7.5.4. Electrocardiogram

Triplicate standard 12-lead ECGs, with readings approximately 1 minute apart, will be recorded as specified in the Schedule of Assessments (Table 1). Patients should be supine for at least 5 minutes before each ECG is obtained. The electrophysiological parameters assessed will be rhythm, ventricular rate, RR interval, PR interval, QRS duration, QT interval, Bazett-corrected QT interval (QTcB), and Fridericia corrected QT interval (QTcF).

When ECG and blood sample collection occur at the same time, ECGs should be performed before blood samples are drawn.

The Investigator or qualified designee will review all ECGs to assess whether the results have changed since the Baseline visit and to determine the clinical significance of the results. These assessments will be recorded on the eCRF. Additional ECGs may be collected at the discretion of the Investigator. Recordings will be archived according to the Study Manual.

7.5.5. Clinical Laboratory Assessments

The following clinical laboratory tests will be evaluated by a central laboratory. Specific instructions for transaminase elevations are provided in Section 6.2.3.1. For any other unexplained clinically relevant abnormal laboratory test occurring after IMP administration, the test should be repeated and followed up at the discretion of the Investigator until it has returned to the normal range or stabilized, and/or a diagnosis is made to adequately explain the abnormality. Additional safety laboratories and assessments as indicated by the clinical situation may be requested. Clinical laboratory assessments are listed in Table 5 and assessments will be assessed as specified in the Schedule of Assessments (Table 1).

While local laboratory results may be used for urgent clinical and dosing decisions, on the day of the clinic visit assessments, all laboratory assessments specified in Table 5 which are performed at the clinic should also be sent in parallel to the central laboratory. In the case of discrepant local and central laboratory results on samples drawn on the same day, central laboratory results will be relied upon for clinical and dosing decisions.

Clinical laboratory assessments may be collected at the clinical site or at home by a trained healthcare professional. It is preferred that clinical laboratory assessments be drawn via peripheral draw (ie, fresh stick), however in cases where peripheral access is not possible existing indwelling venous access may be utilized.

Please see Section 6.2.3.1 for the LFT monitoring and dosing plan.

Table 5: Clinical Laboratory Assessments

| Hematology | |
|---|---|
| Hematocrit | Neutrophils, absolute and % |
| Hemoglobin | Lymphocytes, absolute and % |
| RBC count | Monocytes, absolute and % |
| WBC count | Eosinophils, absolute and % |
| Mean corpuscular volume | Basophils, absolute and % |
| Mean corpuscular hemoglobin | Platelet count |
| Mean corpuscular hemoglobin concentration | CD4 in HIV-positive patients (at Screening only) |
| Serum Chemistry | |
| Sodium | Potassium |
| BUN | Phosphate |
| Creatinine and eGFR (using the MDRD formula) | Albumin |
| Glucose | Calcium |
| Chloride | Carbon dioxide |
| Liver Function Tests (LFTs) | |
| AST | ALP |
| ALT | Bilirubin (total and direct) |
| GGT | |
| Coagulation | |
| Prothrombin time | Activated partial thromboplastin time |
| INR | Fibrinogen |
| D-dimer ^a | Prothrombin fragment 1, 2 |
| Factor Activity | |
| FVIII activity for patients with hemophilia A | FIX activity for patients with hemophilia B |
| Urinalysis | |
| Visual inspection for appearance and color | Bilirubin |
| pH (dipstick) | Nitrite |
| Specific gravity | RBCs |
| Ketones | Urobilinogen |
| Glucose | Leukocytes |
| Protein | Microscopy (if clinically indicated) |

Table 5: Clinical Laboratory Assessments

| Thrombophilia Screening | |
|---|--|
| Protein C deficiency | Protein S deficiency |
| Factor V Leiden (genetic testing) | Prothrombin mutation (genetic testing) |
| Hepatic Tests | |
| Hepatitis A, including: HAV antibody IgM and IgG | Hepatitis C, including: HCV antibody HCV RNA PCR – qualitative and quantitative assays |
| Hepatitis B, including: HBs Ag, anti-HBc antibody, IgM and IgG | Hepatitis E, including: HEV antibody IgM and IgG |
| Immunogenicity | |
| Antidrug Antibodies | |

Note: All assessments will be measured in the central laboratory.

Abbreviations: ALP=alkaline phosphatase; ALT=alanine transaminase; AST=aspartate transaminase; BUN=blood urea nitrogen; CD4=cluster of differentiation 4; eGFR=estimated glomerular filtration rate; FIX=factor IX; FVIII=factor VIII; GGT= gamma glutamyl transferase; HAV=hepatitis A virus; HBs Ag=hepatitis B virus surface antigen; HBc=hepatitis B virus core; HCV=hepatitis C virus; HEV=hepatitis E virus; HIV=human immunodeficiency virus; IgG=immunoglobulin G antibody; IgM=immunoglobulin M antibody; INR=International normalized ratio; MDRD=Modification of Diet in Renal Disease; PCR=polymerase chain reaction; RBC=red blood cell; RNA=ribonucleic acid; WBC=white blood cell.

^a Will not be communicated to investigational sites.

